8.2.5. Post-treatment ARI

Participants must meet criteria for ARI (as defined in [Table 2](#) to be enrolled in the study. Any patient with a clinical response of Resolution (see [Section 8.2.3](#)) at Day 5, 10, or 15 that later experiences new or worsening of ARI symptoms lasting more than 1 day should contact the site staff or investigator to schedule an unplanned post-treatment ARI visit, which should optimally occur within 2 days after the onset of new or worsening symptoms. If the participant is scheduled to have a planned treatment visit or follow-up visit within 3 days of symptom onset of the recurrent ARI, then an unplanned study visit is not necessary.

The purpose of this visit is to perform a clinical assessment and collect a NP swab for virology assessment that can be used to evaluate potential recurrence of RSV infection.

8.2.6. Oxygen Support Details

Type of oxygen support (eg, oxygen supplementation received, mechanical ventilation or ECMO received in hospital) will be collected at baseline and subsequent visits.

8.2.7. Imaging Assessments

Unplanned imaging performed according to routine medical care will be recorded in the source document.

8.2.8. PRO Assessment

8.2.8.1. EQ-5D-5L

EQ-5D is a standardized, validated, generic health related quality of life questionnaire used in clinical and economic HTA evaluations. The questionnaire comprises five questions and covers dimensions of mobility, self-care, usual activities, pain/discomfort, and anxiety/depression. Designed to be self-completed by respondents, the instrument takes a few minutes to complete and is intended to be cognitively undemanding [15-20].

The participant will be invited to complete the questionnaire on an electronic device at the site, and according to the [SoA](#). The first questionnaire should be administered before taking the study drug. If assistance is required to help complete the questionnaire, the site staff should remain neutral and avoid leading participants towards specific answers.

In the suite of EQ-5D instruments developed, the most recent EQ-5D-5L has expanded to a 5-level scale of evaluation compared to the original 3 level evaluation scale. Validation has shown improved reliability and sensitivity of the EQ-5D-5L compared with the original in various diseases. The instrument retains utilities in assessing mobility, self-care, usual activities, pain/discomfort, anxiety/depression and health status using a VAS. The EQ-5D-5L should be completed as described in the [SoA](#), with appropriate training to ensure appropriate measurement at baseline and to limit any potential influence on patient self-assessment during denoted site visits [15-20].

8.2.9. Household Characteristics

Household characteristics will be determined through interview with the participant and may be updated during the study. This assessment is exploratory in nature and will support the characterization of household transmission of acute respiratory infection. The household characteristics include:

- Number of people living in the household.
- Number of additional cases of confirmed or suspected acute respiratory infection among household contacts.
- Number of additional confirmed RSV positive household contacts.

8.3. Safety Assessments

Planned time points for all safety assessments are provided in the [SoA](#). Unscheduled safety measurements may be obtained at any time during the study to assess any perceived safety issues.

8.3.1. Physical Examinations

A general physical examination will be performed by a medically qualified individual (or other authorized delegate) at screening/baseline (see [Table 1](#)) and include, at a minimum, assessments of the cardiovascular, respiratory, gastrointestinal, and neurological systems. Height and weight will also be measured and recorded. Physical examinations conducted at subsequent study visits will be done at discretion of the investigator if the participant has symptoms that need to be evaluated. Investigators should pay special attention to any previously identified or new AE/targeted condition that the participant has experienced.

Physical examination findings collected during the study will be considered source record and will not be required to be reported, unless otherwise noted. Any untoward physical examination findings that are identified during the active collection period and meet the

definition of an AE or SAE ([Appendix 3](#)) must be reported according to the processes in [Section 8.4.1](#) to [Section 8.4.3](#).

8.3.2. Vital Signs

Temperature, pulse rate, respiratory rate, oxygen saturation level, and blood pressure will be assessed as specified in [Table 1](#).

Any untoward vital sign findings that are identified during the active collection period and meet the definition of an AE or SAE ([Appendix 3](#) in [Section 10.3](#)) must be reported according to the processes in [Sections 8.4.1](#) to [8.4.3](#).

8.3.2.1. Blood Pressure and Pulse Rate

BP and PR measurements will be assessed with the participant, in the supine or seated position with their feet on the floor, when possible, with a completely automated device. Manual techniques will be used only if an automated device is not available.

BP and PR measurements should be preceded by at least 5 minutes of rest with the participant in a semisupine or sitting position, in a quiet setting without distractions.

BP and PR will be taken before blood collection for laboratory tests and consist of a single measurement of PR and 3 BP measurements (3 consecutive BP readings will be recorded at intervals of at least 1 minute apart). The average of the 3 BP readings will be recorded on the CRF.

8.3.2.2. Temperature and Respiratory Rate

Temperature (oral, tympanic, axillary, or temporal artery), and respiratory rate, will be assessed and recorded in the CRF.

8.3.2.3. Oxygen Saturation

Oxygen saturation will be assessed as part of the vital signs assessment by a pulse oximeter and recorded in the CRF. Participants who are on chronic oxygen supplementation will be assessed whilst on supplementation.

8.3.3. Electrocardiograms

A single, standard 12-lead ECG will be collected at times specified in the [SoA](#) section of this protocol using an ECG system that automatically calculates the HR and measures PR, QT, QTcF, and QRS intervals. The ECG should be performed after the participant has rested quietly for at least 5 minutes in a supine position.

A qualified medical provider should interpret the 12-Lead ECG used for screening prior to enrollment.

ECG data will be submitted to a central laboratory for measurement and interpretation. The final ECG report from the central laboratory should be maintained in the participant's source

documentation and be the final interpretation of the ECG recording. Any clinically significant changes from the baseline/Day 1 ECG may potentially be AEs ([Appendix 8](#) in [Section 10.8](#)) and should be evaluated further, as clinically warranted.

In some cases, it may be appropriate to repeat abnormal ECGs to rule out improper lead placement as contributing to the ECG abnormality. It is important that leads be placed in the same positions each time in order to achieve precise ECG recordings. If a machine-read QTc value is prolonged, as defined above, repeat measurements may not be necessary if a qualified medical provider's interpretation determines that the QTcF values are in the acceptable range.

ECG values of potential clinical concern are listed in [Appendix 8](#) in [Section 10.8](#).

8.3.3.1. Alternative Facilities for Electrocardiograms

The participant may visit an alternative facility to have the ECGs performed. Qualified study site personnel must order, receive, and review results. ECGs can also be performed through remote device collection.

8.3.4. Clinical Safety Laboratory Assessments

See [Appendix 2](#) ([Section 10.2](#)) for the list of clinical safety laboratory tests to be performed and the [SoA](#) for the timing and frequency. All protocol-required laboratory assessments, as defined in [Appendix 2](#) ([Section 10.2](#)), must be conducted in accordance with the laboratory manual and the [SoA](#). Unscheduled clinical laboratory measurements may be obtained at any time during the study to assess any perceived safety issues.

Laboratory safety parameters will be graded according to the DAIDS Table for Grading the Severity of Adult and Pediatric Adverse Events, version 2.1 [\[21\]](#). The investigator must review the laboratory report, document this review, and record any clinically significant changes occurring during the study in the AE section of the CRF. Clinically significant abnormal laboratory test findings are those that are not associated with the underlying disease, unless judged by the investigator to be more severe than expected for the participant's condition.

All laboratory tests with values considered clinically significant and abnormal during participation in the study or within 28 days of the last dose administration after the last dose of study intervention should be repeated until the values return to normal or baseline or are no longer considered clinically significant by the investigator or study medical monitor.

If such values do not return to normal/baseline within a period of time judged reasonable by the investigator, the etiology should be identified and the sponsor notified.

See [Appendix 6](#) ([Section 10.6](#)) for suggested actions and follow-up assessments in the event of potential DILI.

See [Appendix 7](#) (Section 10.7) for instructions for laboratory testing to monitor kidney function and reporting laboratory test abnormalities.

8.3.4.1. Alternative Facilities for Clinical Safety Laboratory Assessment

Protocol-specified safety laboratory evaluations may be conducted at a local laboratory, during a mobile visit, or at home if permitted by local regulations. The local laboratory may be a standalone institution or within a hospital. The following safety laboratory evaluations may be performed at a local laboratory:

- Hematology
- Biochemistry

If a local laboratory is used, qualified study site personnel must order, receive, and review results. Site staff must collect the local laboratory reference ranges and certifications/ accreditations for filing at the site. Laboratory test results are to be provided to the site staff as soon as possible. The local laboratory reports should be filed in the participant's source documents/medical records. Relevant data from the local laboratory report should be recorded on the CRF.

8.3.5. Pregnancy Testing

A urine or serum pregnancy test is required at screening. Following screening, pregnancy tests may be urine or serum tests, and must have a sensitivity of at least 25 mIU/mL. Pregnancy tests will be performed in WOCBP at the times listed in the [SoA](#).

8.4. Adverse Events, Serious Adverse Events, and Other Safety Reporting

The definitions of an AE and an SAE can be found in [Appendix 3](#) in Section 10.3.

AEs may arise from symptoms or other complaints reported to the investigator by the participant (or, when appropriate, by a caregiver, surrogate, or the participant's legally authorized representative), or they may arise from clinical findings of the investigator or other healthcare providers (clinical signs, test results, etc).

The investigator and any qualified designees are responsible for detecting, documenting, and recording events that meet the definition of an AE or SAE and remain responsible to pursue and obtain adequate information both to determine the outcome and to assess whether the event meets the criteria for classification as an SAE or caused the participant to discontinue the study intervention (see [Section 7.1](#)).

During the active collection period as described in Section 8.3, each participant/legal guardian/legally authorized representative will be questioned about the occurrence of AEs in a nonleading manner.

In addition, the investigator may be requested by Pfizer Safety to obtain specific follow-up information in an expedited fashion.

8.4.1. Time Period and Frequency for Collecting AE and SAE Information

The time period for actively eliciting and collecting AEs and SAEs (“active collection period”) for each participant begins from the time the participant provides informed consent (including the pre-screening informed consent document, if applicable), which is obtained before undergoing any study-related procedure and/or receiving study intervention, through Day 35.

Follow-up by the investigator continues throughout the active collection period and until the AE or SAE or its sequelae resolve or stabilize at a level acceptable to the investigator.

When a clinically important AE remains ongoing at the end of the active collection period, follow-up by the investigator continues until the AE or SAE or its sequelae resolve or stabilize at a level acceptable to the investigator and Pfizer concurs with that assessment.

For participants who are screen failures, the active collection period ends when screen failure status is determined. For participants who provide pre-screening informed consent, the active collection period ends 30 minutes after collection of the pre-screening viral testing or once viral testing results become available, whichever occurs first.

If the participant withdraws from the study and also withdraws consent for the collection of future information, the active collection period ends when consent is withdrawn.

If a participant permanently discontinues or temporarily discontinues study intervention because of an AE or SAE, the AE or SAE must be recorded on the CRF and the SAE reported using the CT SAE Report Form.

Investigators are not obligated to actively seek information on AEs or SAEs after the participant has concluded study participation. However, if the investigator learns of any SAE, including a death, at any time after a participant has concluded study participation, and they consider the event to be reasonably related to the study intervention, the investigator must promptly report the SAE to Pfizer using the CT SAE Report Form.

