Total duration of study participation for each participant is approximatively 5 weeks (Day 35 ± 2 days) divided as follows:

- Screening and Randomization procedures can be on the same day or over two consecutive days. The participant must be randomized by the second day (Day 1 of study intervention).
- A 5-day dosing period; If the first dose of study intervention is administered at a time that would only allow one dose to be taken on Day 1, the dosing period will continue until Day 6 to allow for a total of **CC** doses.
- A 4-week follow-up period after the last study intervention dose.

Study Intervention(s)		
Intervention Name	Sisunatovir CCI mg	Placebo
Use	Experimental	Placebo
IMP or NIMP/AxMP	Investigational medicinal product (IMP)	IMP
Dose Formulation	tablet	tablet
Unit Dose Strength(s)	100 mg	0 mg
Route of Administration	Oral	Oral
Study Arm(s)		
Arm Title	Sisunatovir	Placebo
Arm Description	Participants will receive CCI tablets of 100 mg of sisunatovir CCI from Day 1 to Day 5 (CCI doses).	Participants will receive CCI matching placebo tablets CCI from Day 1 to Day 5 (CCI doses).

Statistical Methods:

The primary estimand is the difference in treatment proportions of participants experiencing RSV-related hospitalization or death from any cause through Day 28 in non-hospitalized adults with RSV infection who are at increased risk of progression to severe illness. This will be estimated irrespective of compliance to the planned course of treatment or use of concomitant medications.

The primary analysis will also be conducted for the two planned efficacy IAs. Two-sided 95% CI (adjusted for the planned IAs) and associated p-value for the null hypothesis of no difference between treatment groups will be presented. Significance level for the primary assessment of efficacy will be determined using the CCI h at the second efficacy IA and the final analysis. Significance level for assessment of futility will be determined using the CCI approach at the first and second efficacy IAs. The overall significance level is set at 2.5% (1 sided).

This study is designed to have 90% statistical power to show a difference between the treatment arms (sisunatovir versus placebo) of CCI% in the proportion of participants hospitalized/dying, using a 1-sided Type I error rate of 2.5%. The proportion of hospitalization/death in the placebo arm is assumed to be CCI%. A CCI% absolute difference represents a CCI% relative reduction from placebo.

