1.2. Schema

Informed consent & Screening	1:1 Randomization	Treatment	Follow-Up**			
		Sisunatovir CC1 mg PO CC1 OR Placebo				
Days -1 to 1	Day 1	Day 1 to Day 5* (Treatment Duration: 5 days) Study Visits on Days 1, 3 and 5	± 1 Day	± 2 Day	± 2 Days	± 2 Days
			F/U 1 Day 10	F/U 2 Day 15	F/U 3 Day 28	F/U 4 (phone) Day 35

*Treatment duration to extend into Day 6 if the first dose is taken in the evening of Day 1.

** An unplanned visit for post-treatment ARI can be conducted between Day 6 to Day 28.

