4.4. End of Study Definition

The end of the study is defined as the date of the last scheduled visit (Day 35) of the last participant in the study or the last scheduled procedure shown in the **SoA** for the last participant in the trial globally.

A participant is considered to have completed the study if they have completed all periods of the study, including the last scheduled visit (Day 35) shown in the **SoA**.

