6.1.1. Administration

Participants will be dispensed 1 bottle of sisunatovir or matching placebo. Participants will take CCI tablets of sisunatovir or matching placebo every CCI (dose of CCI mg; total daily dose of CCI mg) for a total of CCI doses (5 days or 6 days if only one dose was taken on Day 1).

Participants should take the first dose of study intervention on Day 1, preferably during the in-person visit or as soon as possible after randomization. To allow the participant to select a convenient CCI dosing schedule, timing of dosing for the second dose may be adjusted slightly but should be taken at least CCI but no later than CCI after the first dose. The remaining doses should be taken every CCI

Participants will swallow the study intervention whole and will not manipulate or chew the study intervention prior to swallowing. Participants should take the study intervention [REDACTED] CCI [REDACTED] Refer to the IP Manual for additional dosing and administration instructions. Whether or not the participant had [REDACTED] CCI [REDACTED] before taking study intervention will be collected.

If a dose is delayed, it should be taken as soon as possible, but no later than [REDACTED] CCI [REDACTED] before the next scheduled dose. Participants should not double up the next dose of study drug to “make up” what had been missed. Dosing should be stopped at the end of the treatment period [REDACTED] CCI doses total). Any remaining tablets at the end of 5 days (or 6 days if only one dose was administered on Day 1) must be returned at the next study visit.

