8.4.5.1. Exposure During Pregnancy

An EDP occurs if:

- A female participant is found to be pregnant while receiving or after discontinuing study intervention.
- A male participant who is receiving or has discontinued study intervention inseminates a female partner.
- A female nonparticipant is found to be pregnant while being exposed or having been exposed to study intervention because of environmental exposure. Below are examples of environmental EDP:
 - A female family member or healthcare provider reports that she is pregnant after having been exposed to the study intervention by ingestion.
 - A male family member or healthcare provider who has been exposed to the study intervention by ingestion then inseminates his female partner prior to or around the time of conception.

The investigator must report EDP to Pfizer Safety within 24 hours of the investigator's awareness, irrespective of whether an SAE has occurred. The initial information submitted should include the anticipated date of delivery (see below for information related to termination of pregnancy).

- If EDP occurs in a participant or participant's partner, the investigator must report this information to Pfizer Safety using the CT SAE Report Form and an EDP Supplemental Form, regardless of whether an SAE has occurred. Details of the pregnancy will be collected after the start of study intervention and until a minimum of 28 calendar days after the last administration of study intervention.

- If EDP occurs in the setting of environmental exposure, the investigator must report information to Pfizer Safety using the CT SAE Report Form and an EDP Supplemental Form. Since the exposure information does not pertain to the participant enrolled in the study, the information is not recorded on a CRF; however, a copy of the completed report is maintained in the investigator site file.

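### The final safety call may be made on Day 33 or 34, before AE/SAE collection ends on Day 35; only for Day 6 finishers called on Day 33 is post-dose follow-up also one day short of 28 days

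*Protocol*

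**What the plan says.** Protocol section 8.4.1 starts active elicitation of AEs and SAEs at informed consent, "which is obtained before undergoing any study-related procedure and/or receiving study intervention, through Day 35". The safety endpoints in Protocol section 3 and SAP section 3.2.2.1 are the proportions of participants with TEAEs and with SAEs through that same day.

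The schema shows the last contact as "F/U 4 (phone) Day 35". The schedule of activities (Table 1) and the schema both give it a window of ±2 days. The synopsis puts the same tolerance on participation as a whole: "Total duration of study participation for each participant is approximatively 5 weeks (Day 35 ± 2 days) divided as follows". The list that follows includes a 4-week follow-up after the last dose.

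On dosing, section 6.1.1 allows "5 days or 6 days if only one dose was taken on Day 1", and the synopsis says that in this case "the dosing period will continue until Day 6 to allow for a total of" the planned number of doses. Section 8.4.5.1 has pregnancy details collected "until a minimum of 28 calendar days after the last administration of study intervention".

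Two further rules fix what happens around the call. Section 4.4 counts the Day 35 visit as the last element of study completion. Section 8.4.1 releases investigators from actively looking for events once participation has ended; after that, only SAEs that come to their attention and that they judge reasonably related must be reported.

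**The concern.** The collection period and the endpoints end on a fixed day, but the contact meant to close them may fall up to two days earlier. No later contact is scheduled. For a participant called early, the last one or two days are inside the endpoint's time frame but are not covered by any planned question.

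A second mismatch concerns time since the last dose. The synopsis list allows dosing into Day 6, ends participation at Day 35 ± 2, and promises four weeks of follow-up after the last dose. At one combination of permitted days these three statements cannot all hold, and the pregnancy minimum in section 8.4.5.1 is missed at the same point.

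What is at stake is how accurately the safety endpoints are labelled and whether the schedule delivers the follow-up that the protocol states. The efficacy analysis is not affected.

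**Working it through.** **Inputs**
- End of active AE/SAE collection: Day 35 (Protocol 8.4.1).
- Final contact: Day 35 ± 2, so Days 33 to 37 (Table 1, schema, synopsis).
- Last dose: Day 5, or Day 6 if only one dose was taken on Day 1 (synopsis, schema, 6.1.1).
- Required time after the last dose: 4 weeks (synopsis) and 28 calendar days for pregnancy details (8.4.5.1).

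**Formulas**
- Days of AE/SAE collection not covered = max(0, 35 − contact day).
- Days after last dose = contact day − last-dose day.
- Shortfall against 28 = max(0, 28 − days after last dose).

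**The plan's own figure.** With the call on Day 35 itself, follow-up is 35 − 5 = 30 days or 35 − 6 = 29 days. The stated four weeks are met in both cases.

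**Across the permitted window**

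| Call on | AE/SAE days not covered | Days after a Day 5 last dose | Days after a Day 6 last dose |
|---|---|---|---|
| Day 33 | 2 | 28 | 27 (1 short) |
| Day 34 | 1 | 29 | 28 |
| Day 35 | 0 | 30 | 29 |
| Day 36 | 0 | 31 | 30 |
| Day 37 | 0 | 32 | 31 |

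The AE/SAE gap does not depend on when dosing ended: anyone called on Day 33 or 34 has it, and it is at most 2 of 35 days. The post-dose shortfall appears in one cell only, Day 6 finishers called on Day 33, and it is one day.

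**With a 0/+2 window** only the last three rows remain. The AE/SAE gap is 0, and follow-up after the last dose is at least 30 days (Day 5) or 29 days (Day 6).

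**The case against.** The best reply is that Day 35 is a visit label with a stated tolerance. The synopsis attaches ±2 days to the whole of participation, and sections 4.4, 6.4.2 and 6.4.3 speak of Day 35 as a visit. On that reading, collection through Day 35 means through the Day 35 contact, and the AE/SAE half is an ambiguity of wording. This has force, but it leaves observation ending anywhere from Day 33 to Day 37 under an endpoint that names Day 35. The SAP does not settle it: its TEAE definition has a start rule and no upper limit. The reading also does nothing for the 27-day case, because the 28-day minimum is counted from the last dose.

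A second reply is that section 4.4 is met only when "A participant is considered to have completed the study if they have completed all periods of the study, including the last scheduled visit (Day 35") has been completed. The periods include safety follow-up through Day 35, so a Day 33 call may not by itself conclude participation. That is arguable, but no contact is scheduled after the call, so planned elicitation has still stopped.

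Third, capture does not stop altogether. Section 8.4.1.2 requires spontaneously reported events to be recorded, section 8.1.2 has participants reminded to report changes in health promptly, and related SAEs remain reportable at any time. This stands: what is missing is one planned question covering one or two days.

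Fourth, a reader might infer that a Day 33 call cuts the pregnancy period short for everyone, or that pregnancies would be lost. The documents do not support that. Day 5 finishers reach exactly 28 days, the duty in section 8.4.5.1 is not tied to the call, and known pregnancies are followed to completion. The possible gap is in asking about a pregnancy not yet known, and the last scheduled pregnancy test is at Day 15 in any case.

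**Conclusion.** The point holds as a minor inconsistency. Calls on Day 33 or 34 leave 2 or 1 days of the stated AE/SAE period without planned elicitation. Separately, Day 6 finishers called on exactly Day 33 have 27 days after the last dose against a stated 28.

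The 27-day figure counts the day after the last dose as day 1, which is the natural sense of days after a dose. Counting the dose day itself would give 33 − 6 + 1 = 28 and remove that shortfall, but not the AE/SAE gap.

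A reader might go further and put a share on the participants affected. If calls were spread evenly over the five permitted days, 2/5 = 40% would be called early, with a mean loss of (2 + 1 + 0 + 0 + 0)/5 = 0.6 days. The documents give no distribution of call dates, so neither figure can be asserted. Depending on practice, the share could lie anywhere from none to all.

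Nor is there support for a biased comparison. The window is the same in both arms, the trial is double-blind, and Protocol section 9.3.5 plans no formal testing of safety data. The practical effect is smaller still because, according to SAP section 2.1, the study was discontinued with very few participants.

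**What to change.** Change the window of the Day 35 contact from ±2 to 0/+2 days in Table 1, the schema and the synopsis, and keep Day 35 as the last day on which TEAEs and SAEs are counted for the endpoints. The cut-off should be written into the SAP's TEAE and SAE definitions, so that calls on Day 36 or 37 do not lengthen the counting period for some participants.

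This adds no visit, procedure or participant. The cost is two fewer days of flexibility for a telephone call.

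Rewording section 8.4.1 to end at the Day 35 contact would be cheaper and would settle the AE/SAE text, but it would leave the 27-day case. A call no earlier than Day 34 would meet the 28-day minimum but leave one day of AE/SAE collection uncovered. The 0/+2 window closes both.

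If the protocol can no longer be amended, the study report can state the Day 35 counting rule and give, by arm, the number of final contacts made before Day 35.
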